### ***7.3.1.3 Discontinuations Due To Treatment Emergent Adverse Events***

Similar tables to that for serious TEAEs will be produced for all discontinuations due to TEAEs to Day 90 (Tables 14.3.1.8.1.1 and 14.3.1.8.2.1), Day 180 (Tables 14.3.1.8.1.2 and 14.3.1.8.2.2) and Day 360 (Tables 14.3.1.8.1.3 and 14.3.1.8.2.3).

### ***7.3.1.4 Deaths***

Similar tables to that for serious TEAEs will be produced for deaths to Day 90 (Tables 14.3.1.9.1.1 and 14.3.1.9.2.1), Day 180 (Tables 14.3.1.9.1.2 and 14.3.1.9.2.2) and Day 360 (Tables 14.3.1.9.1.3 and 14.3.1.9.2.3).

A supporting categorical summary will also be presented using other collected data. These include: Time of death after randomisation (days), Location (ICU or hospital) at the Time of death (Patient Status (i.e.: partly a repeat of Patient Status data in section 6.6.1)) and Cause of death (Death Report at Day 180 or Day 360) (Table 14.3.1.10).

### ***7.3.2 Vital Signs***

Vital signs are recorded at Day 1 (Pre-dose), then at selected visits (Day 2 - 28 (In/Out Of ICU), Last day in ICU) and in the event of withdrawal, at Early Termination. The Last observation performed is also derived.

Blood pressure (systolic/diastolic), Mean arterial pressure, Heart rate, Body temperature and total respiratory rate measured will be summarised numerically for each Treatment group and Severity of ARDS (Moderate/Severe) at each assessment time (i.e.: Each Day in ICU and including Last observation performed) using the actual values and change from baseline (Tables 14.3.2).

### ***7.3.3 Twelve Lead ECG***

ECG are recorded are performed at Day 1 (Pre-dose) then on Day 7. Ventricular rate, PR, PQ Interval, QRS Duration and QTc will be summarised numerically for each Treatment group and Severity of ARDS at both assessment times (Day in ICU) using the actual values and change from baseline (Tables 14.3.3.1).

A categorical summary will be used for the overall Normal/Abnormal NCS/Abnormal CS result (Table 14.3.3.2).

### ***7.3.4 Physical Examination***

The Physical examination findings will be displayed as categorical summaries at each assessment time.

Physical examinations are performed at Screening, then at the Last day in ICU and Day 28 (Out of ICU) or Early Termination. The Last observation performed is derived. Major body systems: General appearance, Ear, nose and throat, Eyes, Respiratory, Abdomen, Urogenital, Musculoskeletal, Neurological, Lymph nodes and Skin will be categorically summarised for each Treatment group and overall and Severity of ARDS at each assessment time (Day in ICU) (Tables 14.3.4).

Predicted body weight at screening will be summarised with other demographics.

### ***7.3.5 Laboratory Assessments***

Laboratory assessments are performed at Day 1 (Pre-dose) and Day 2 - 28 (In/Out Of ICU), Last day in ICU) or at Early Termination. The Last observation performed is derived. Actual values and within patient Change from baseline (for numeric variables) for all haematology, chemistry and urinalysis will only be listed with patients identified by Treatment group, Severity of ARDS, Country and Investigational site for each assessment time using the Safety population.

Laboratory values are also classified by the Investigator as Out of range (Not clinically significant), Out of range (Clinically significant) or Out of range (Clinically significant and an Adverse event). Categorical summaries for these data will be pooled over all sites and identified according to Treatment group but not by Severity of ARDS or by Country. These summary tables will also contain Normal and Not Done (including missing) categories for comparative purposes (Tables 14.3.5.1.1, Haematology; Tables 14.3.5.2.1, Biochemistry; Urinalysis, Tables 14.3.5.3.1).

Source laboratory normal ranges for these classifications will also be presented as listings for each of the Investigational sites.

Shift tables displaying the overall change from baseline (Day 1 Pre-dose) in these categorical classifications (Out of range (Not clinically significant), Out of range (Clinically significant) or Out of range (Clinically significant and an Adverse event)) will be provided according to Treatment group for each laboratory variable relating the Last observation performed during the 28 day period in the ICU. These shift tables will also contain Normal and Not Done (including missing) categories for comparative purposes (Tables 14.3.5.4.1, Haematology; Tables 14.3.5.5.1, Biochemistry; Urinalysis, Tables 14.3.5.6.1).

Supporting listings for all the laboratory variables for each patient and each assessment time will include the actual values, clinical classification and any comments on the clinical significance of findings. Patient identifiers of Treatment group, Severity of ARDS, Country and Investigational site will be included. Additional (Unscheduled) laboratory assessments performed will only be listed.

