### 5.2 Administration

FP-1201-lyo 10 µg (or placebo) will be diluted in WFI near the patient/in the ICU. Once prepared, the dose must be administered to the patient immediately. The diluted FP-1201-lyo or placebo will be administered as an intravenous bolus injection via a central or peripheral line. The injection will be followed with a 5 mL flush of sterile saline (not provided).

FP-1201-lyo and placebo injections will be given once daily for 6 days. The injection should be given at the same time each day  $\pm 1$  hour providing the patient's condition allows this. If for any reason this is not possible, the treatment window may be extended by up to 4 hours. The reason for the delay must be entered in the e-CRF. Subsequent doses should not be delayed and should revert to the original time schedule (e.g., if the D1 dose was at 13:00, the D2 dose was delayed and given at 17:00, the D3 dose should be given at 13:00  $\pm 1$  hour).

No dose modifications or temporary cessations of study drug administration are allowed. If a delay beyond the 4-hour window described above is required, the patient must be withdrawn from study drug but all data must continue to be collected per protocol. Administration of a second course of study drug is not permitted.

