### 6.2.2 Laboratory Variables

The biochemistry and haematology analysis will be performed at the hospital laboratories of the individual Investigator sites. Copies of laboratory accreditation and relevant reference ranges will be provided to the Sponsor or representative prior to the analysis of the first patient sample at that site.

The laboratory variables measured in the study will be as detailed in Table 3.

Blood samples for determination of biochemistry and haematology will be taken at screening, pre-dose on D1 (baseline value) and daily up to D28 while the patient is in the ICU, as detailed in the Schedule of Procedures in Section 7.1, Table 5. The date and time of sample collection will be recorded in the e-CRF.

Dipstick urinalysis will be taken in the ICU (if urine is being produced) pre-dose on D1 (baseline value) and daily up to D28 while the patient is in the ICU, as detailed in the Schedule of Procedures in Section 7.1, Table 5. The date and time of sample collection will be recorded in the e-CRF.

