### **8.6.2 Vital Signs**

Vital signs data (BP, HR and temperature) will be summarised using descriptive statistics (mean, median, SD, minimum and maximum) by treatment group separately at D1 and daily to D28. The maximum change from baseline over the 28-day follow-up period will be calculated for each patient and summarised.

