### **8.6.3 Clinical Laboratory and Urinalysis Variables**

Descriptive statistics (mean, median, SD, minimum and maximum) for biochemistry and haematology variables will be obtained and tabulated by treatment group pre-dose on D1 and daily to D28. Number and percentage will be obtained for each category for urinalysis and tabulated by treatment group at the same time points.

Shift tables (within, below and above the normal range) will also be provided for each parameter in relation to the maximum change from baseline from D1 over the complete 28-day follow-up period.

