### ***5.9.6 Strategy For Missing Data***

No biases resulting from missing data are anticipated and, as a consequence No imputation of any missing values at any of the assessments performed is planned.

However, to allow for patient attrition or any changes to the scheduled patient assessments as a consequence of the treatment response a 'Last observation performed' assessment will be derived for specific Short term efficacy (Ventilation assessment, System Organ Failure (SOFA), Cardiovascular, Pulmonary and Renal function), Pharmacodynamic (IFN $\beta$  ADA & Nab, MxA, CD73, PIM) and Safety variables (Vital signs and Laboratory assessments). This approach will use the last available non-missing post baseline value.

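### SAP 7.3.5 builds laboratory shift tables on the last ICU observation, not the protocol's maximum change over 28 days, so an abnormality that arises during dosing and resolves shows as no shift

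*SAP*

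**What the plan says.** **Laboratory data.** Protocol 8.6.3 specifies both the categories and the value to be used. The categories are set here: "Shift tables (within, below and above the normal range) will also be provided for each parameter". The value is the largest departure, "in relation to the maximum change from baseline from D1 over the complete 28-day follow-up period". The same section also plans daily descriptive statistics by arm.

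SAP 7.3.5 plans shift tables by arm that start from Day 1 pre-dose and are described as "relating the Last observation performed during the 28 day period in the ICU". SAP 5.9.6 defines that observation: "This approach will use the last available non-missing post baseline value". The categories become the investigator's significance classes (out of range and not significant, significant, or significant and an adverse event), plus normal and not done. Numeric values and changes from baseline are listed only.

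**Vital signs.** Protocol 8.6.2 states: "The maximum change from baseline over the 28-day follow-up period will be calculated for each patient and summarised". SAP 5.8.1 and 7.3.2 plan actual values and changes from baseline for each day in ICU and for the last observation. Neither mentions a per-patient maximum.

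The SAP introduction says that the plan is based on Protocol v6.0. Neither change is acknowledged or explained.

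**The concern.** A shift table is the usual place to look for how many patients in each arm moved from an acceptable laboratory value to an abnormal one. In this trial the drug is given for a short time at the start and follow-up is much longer. The protocol's own background points to laboratory tests as worth watching: minor haematology and chemistry changes in the monkey study (1.1.2), and clinically significant low haemoglobin in all Phase I/II cohorts, although also at screening. A table built on the final value describes how patients left the ICU. It does not describe what happened while they were being dosed.

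The timing of the final value also depends on outcome. It is taken at ICU discharge, withdrawal or D28, or is the last sample before death. If the drug affects survival or discharge, the arms are compared at systematically different moments.

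**Working it through.** No figure in the plan needs to be reproduced. The check compares the two rules and then works out what each one uses.

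| | Protocol 8.6.2 and 8.6.3 | SAP 5.8.1, 5.9.6, 7.3.2, 7.3.5 |
|---|---|---|
| Laboratory shift: value used | Maximum change over 28 days | Last non-missing post-baseline value |
| Laboratory shift: categories | Below, within, above range | Investigator significance classes, no direction |
| Numeric laboratory data | Daily summaries by arm | Listed only |
| Vital signs, daily by arm | Yes | Yes |
| Vital signs, per-patient maximum | Yes | Not mentioned |

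**Inputs.**
- Dosing (Protocol 5.2): "FP-1201-lyo and placebo injections will be given once daily for 6 days", that is D1 to D6.
- Sampling (Protocol 6.2.2): "pre-dose on D1 (baseline value) and daily up to D28 while the patient is in the ICU".

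**What the SAP rule uses.** Let L be the day of a patient's last laboratory value.
- Post-baseline sampling days available = L − 1. For L = 28 this is 28 − 1 = 27, of which the table uses 1.
- Gap from last scheduled dose to the tabulated value = L − 6. For L = 28 this is 28 − 6 = 22 days, the ceiling. For a patient discharged on D10 it is 10 − 6 = 4 days. For a death on or before D6 there is no gap.
- For every patient with L > 6, no value taken on D1 to D6 enters the table.

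**Illustrative patient (assumed).** Normal at baseline, out of range and clinically significant on D3 to D6, normal from D7 to the last observation. The SAP table records normal to normal. Under the protocol rule, if the D3 to D6 values are the patient's largest departure from baseline, the patient is shown as moving out of range, with the direction. If the abnormality only partly resolves, the SAP table shows a smaller shift rather than none.

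**Comparison between arms.** The sample-size section (Protocol 8.10) assumes D28 mortality of 30% on control and 15% on active drug. If that held, the share of patients whose last value precedes death could differ by up to 30 − 15 = 15 percentage points. It would differ by less where deaths occur after the last laboratory sample in ICU. Pre-death values would then weigh more heavily in the control table and recovered values in the active one.

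**Is there a stated reason?** SAP 5.8.5 cites differences between local laboratories in assays, units and ranges, and restricts numeric values to within-patient changes. That bears on pooling raw values. It does not explain preferring the last value, because a per-patient maximum is also a within-patient change.

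**The case against.** The strongest reply is that little is actually lost. Every laboratory value and classification is listed. Abnormalities reported as adverse events enter the treatment-emergent tables whenever they resolve. SAP 7.3.5 also plans categorical summaries of the investigator classes by arm. The safety outputs are descriptive (SAP 6.3), no test or endpoint depends on the shift table, and the IDMC sees unblinded safety data during the trial. Most of this stands and it limits the size of the point. Two qualifications apply:
- The adverse event tables are an incomplete backstop. Protocol 6.2.1.3 says that common ICU aberrations are not necessarily adverse events. Section 6.2.1.3.4 excludes significant findings associated with the disease unless they are judged more severe than expected.
- The text does not say whether the categorical summaries are by day, and the table shells in SAP Appendix 1 are not in the available text. Daily counts, if that is what they are, would still not give each patient's worst shift.

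A reader might infer that transient temperature changes also disappear from a shift table. The documents do not support this. Neither plans a shift table for temperature, and SAP 7.3.2 summarises it by arm for each ICU day. Only the per-patient maximum is missing.

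A worst-value table has its own weakness. A patient whose last sample is on D7 contributes 7 − 1 = 6 post-baseline days and one sampled to D28 contributes 27, so longer stays have more chances of an abnormal worst value. That is a reason for careful reading, not for replacing the protocol's table.

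**Conclusion.** The SAP departs from the protocol in two safety outputs without giving a reason. In the laboratory shift tables, an abnormality that arises during D1 to D6 and returns to its baseline class before the last observation appears as no shift. The change of categories also removes the direction. For vital signs, the omission is confined to the per-patient maximum.

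The 22-day gap is an upper limit, and the documents give no basis for estimating how many patients would be affected. It would go too far to say that such events vanish from the report, or that no other summary could reveal them: the listings, the adverse event tables and possibly the categorical summaries remain. The conclusion rests on the SAP text as written. Shells containing a worst-value shift table would remove the laboratory part. The primary and other efficacy analyses are unaffected.

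**What to change.** Before the Day 90 database lock:
- Add laboratory shift tables by arm from baseline to the maximum-change (worst) post-baseline value up to D28, classed as below, within or above each site's own normal range. SAP 7.3.5 already plans to list those ranges by site. Classing each value against its local range avoids pooling units across laboratories.
- Define the derivation. The protocol does not say whether maximum means the largest absolute change or the largest rise and fall taken separately. Where both directions matter, tabulating the highest and lowest values separately keeps the direction.
- Add a worst investigator-classification version if wanted. It cannot replace the range-based table, because it carries no direction.
- Add the per-patient maximum change from baseline for vital signs.
- Keep the last-observation tables as supplementary, and present length of ICU stay by arm beside the worst-value tables.

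If the sponsor prefers the last-observation rule alone, the SAP should say so and justify it before unblinding. Protocol section 8 in any case requires deviations from planned analyses to be justified in the final report.

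The cost is SAP wording, extra shells and one additional derivation per parameter. No new data are needed.

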#### ***7.4 Addendums Long Term (Day 180) & Extended Follow Up (Day 360) Efficacy And Safety Report***

Data collected at Day 180 (Day 90 to Day 180) encompassing the long term follow up and Day 360 encompassing the Extended Follow Up period (Day 180 to Day 360) will be summarised separately and issued as an addendum to the Clinical Study Report (CSR). However, where appropriate any available safety data will be presented in the main report at Day 90 and/or Day 180 addendum report.

But, new table summaries will be generated and separate statistical analyses performed with the additional information available where appropriate. This applies to: Patient Status (+Mortality rate Day 180/360), Quality of life (EQ-5D-3L), Respiratory functioning (FEV-1) and Neurological functioning (6MWT).

The Overall survival rate (Time to Death) analysis will also be updated and relevant tables and figures regenerated.

Other specific table summaries relating to previously reported data will be regenerated after updating the database. This applies to: Patient Completion and Unblinding details plus all AEs and Death reports.

Table shells for the long term and extended follow up periods are given in Appendix 5 and 6, respectively.

#### ***7.5 Graphical Presentations***

Key findings identified in summary and analysis tables will be presented graphically. A complete list with template shells are given in Appendix 2.

Template type 1 will present individual treatment estimates for FP-1201-lyo and placebo. Type 2 will present FP-1201-lyo - placebo differences or FP-1201-lyo / placebo ratios. Variability (95% CI) of all estimates will be indicated.

#### ***7.6 Data Listings***

All data presented in summary tables will be supported by specific referenced data listings. These will identify the Patient number, Investigator site, Country id, Treatment, Visit/Day/Dose number and provide actual data and/or derived data as appropriate.

The following listings will be included in the Day 90 report only:

- Listing 16.2.1.6: ICU Admission
- Listing 16.2.1.8: Demographics
- Listing 16.2.1.9 APACHE II Scores
- Listing 16.2.1.10: Disease Diagnosis
- Listing 16.2.1.11: Medical History
- Listing 16.2.1.12: Prior Medications
- Listing 16.2.1.16: Pregnancy Test

- Listing 16.2.1.17.1: Inclusion Criteria – Part 1
- Listing 16.2.1.17.2: Inclusion Criteria – Part 2
- Listing 16.2.1.18.1: Exclusion Criteria - Part 1
- Listing 16.2.1.18.2: Exclusion Criteria - Part 2
- Listing 16.2.1.19: X-Ray Selected
- Listing 16.2.1.20: Eligibility Criteria
- Listing 16.2.1.21: Randomisation
- Listing 16.2.1.22: Drug Administration
- Listing 16.2.2.2: Externally Transferred Patients - Day 28 No Longer in ICU
- Listing 16.2.2.3: Patient Status Score Derivations
- Listing 16.2.2.4: SOFA
- Listing 16.2.2.5: Ventilation Parameters
- Listing 16.2.2.6: Fluid Balance
- Listing 16.2.2.15.1: Blood Sampling for Biomarkers - IFN $\beta$  BAb and NAb
- Listing 16.2.2.15.2: Blood Sampling for Biomarkers – MxA
- Listing 16.2.2.15.3: Blood Sampling for Biomarkers - CD73
- Listing 16.2.2.15.4: Blood Sampling for Biomarkers – PIMs
- Listing 16.2.3.3: Electrocardiogram (Safety Population)
- Listing 16.2.3.4: Physical Examination at Screening
- Listing 16.2.3.5: Physical Examination Changes

The following listings will be included in the Day 90 report **and subsequently updated** and presented again in the Day 180 and 360 addendums:

- Listing 16.2.1.1.3: Patient Disposition (All Patients) - Death Reports
- Listing 16.2.1.4: Deviations Day 90 Report ((All Patients))
- Listing 16.2.1.5: Comments
- Listing 16.2.1.7: Visit Dates
- Listing 16.2.1.13: Infusion Concomitant Medications - Parts 1 – 2
- Listing 16.2.1.14: Bolus Concomitant Medications - Parts 1 – 2
- Listing 16.2.1.15: Vasoactive Medications
- Listing 16.2.2.1.1: Patient Status - Deaths (Safety Population)
- Listing 16.2.2.1.2: Patient Status - Ventilation, Renal and Vasoactive Support
- Listing 16.2.2.7: Procedures, Interventions, Surgeries and Diagnostics
- Listing 16.2.3.1: Adverse Events Listing (Safety Population)
- Listing 16.2.3.6.1: Laboratory Values – Haematology (for unscheduled visits only)
- Listing 16.2.3.6.2: Laboratory Values – Chemistry (for unscheduled visits only)
- Listing 16.2.3.6.3: Laboratory Values – Urinalysis (for unscheduled visits only)

The following listings supporting data collected only at Days 180 and 360 will be included in the addendum reports only:

- Listing 16.2.1.1.1: Patient Disposition (All Patients) - Completion and Withdrawal Day 180
- Listing 16.2.1.1.2: Patient Disposition (All Patients) - Completion and Withdrawal Day 360
- Listing 16.2.2.8: EQ-5D-3L Assessment
- Listing 16.2.2.9: FEV

- Listing 16.2.2.10: Investigator's Evaluation Form for 6MWT
- Listing 16.2.2.11: 6MWT Concomitant Medications
- Listing 16.2.2.12: 6MWT Comorbidities
- Listing 16.2.2.13.1: 6MWT Pre First Test Recordings
- Listing 16.2.2.13.2: 6MWT During the First Test Recordings
- Listing 16.2.2.13.3: 6MWT After the First Test Recordings
- Listing 16.2.2.14.1: 6MWT Pre Second Test Recordings
- Listing 16.2.2.14.2: 6MWT During the Second Test Recordings
- Listing 16.2.2.14.3: 6MWT After the Second Test Recordings

Listings will be created according to the ICH guidelines, as appropriate for the data collected.

---

## **9. Finalisation of Statistical Analysis Plan**

The statistical analysis plan, and all relevant table, figures and listing ‘shells’ will be finalised before database lock – Day 90 CSR.

---

## **10. Appendices to be Included in the Statistical Report**

1. Summary tables
  2. Figures
  3. Listings supporting summary tables
  4. Data derivations – contains rules for deriving efficacy variables when required
  5. Long Term Follow Up Day 180 = Summary tables, figures and supporting listing  
(Addendum to report)
  6. Extended Long Term Follow Up Day 360 = Summary tables, figures and supporting listing  
(Addendum to report)
-
